## **5.2 Enrollment and Retention of Study Population**

### **5.2.1 Recruitment Procedures**

Subjects may be recruited from the general population. The sites will ensure that any advertisements used to recruit subjects (letters, pamphlets, posters, etc.) are submitted to Sanofi Pasteur prior to submission to the IEC / IRB for approval.

### **5.2.2 Informed Consent Procedures**

Informed consent is the process by which a subject's parent / guardian voluntarily confirms his or her willingness to participate in a particular study. Informed consent must be obtained before any study procedures are performed. The process is documented by means of a written, signed, and dated ICF.

In addition to the ICF, subjects that are 7 years of age and older will be asked to review and sign a separate assent form.

In accordance with GCP, prior to signing and dating the consent form, the subject's parent / guardian must be informed by appropriate study personnel about all aspects of the study that are relevant to making the decision to participate and must have sufficient time and opportunity to ask any questions. A subject whose parent / guardian cannot read will not be included in the study.

The actual ICF used at each center may differ, depending on local regulations and IEC / IRB requirements. However, all versions must contain the standard information found in the sample ICF provided by the Sponsor. Any change to the content of the ICF must be approved by the Sponsor and the IEC / IRB prior to the form being used.

If new information becomes available that may be relevant to the subject / subject's parent's / guardian's willingness to continue participation in the study, this will be communicated to him / her in a timely manner. Such information will be provided via a revised ICF or an addendum to the original ICF.

Informed consent forms will be provided in duplicate, or a photocopy of the signed consent will be made. The original will be kept by the Investigator, and the copy will be kept by the subject / subject's parent / guardian.

Documentation of the consent process should be recorded in the source documents.

### **5.2.3 Screening Criteria**

There are no screening criteria other than the inclusion and exclusion criteria.

### **5.2.4 Inclusion Criteria**

An individual must fulfill *all* of the following criteria to be eligible for study enrollment:

- 1) Aged 6 months to 17 years on the day of inclusiona.
- 2) Assent form has been signed and dated by the subject (7 to 17 years of age) and informed consent form has been signed and dated by the parent(s) or guardian(s) and by an independent witness, if required by local regulations.
- 3) Subject and parent / guardian are able to attend all scheduled visits and to comply with all study procedures.
- 4) For subjects aged < 24 months: Born at full term of pregnancy ( $\geq 37$  weeks) and/or with a birth weight  $\geq 2.5$  kg.

### **5.2.5 Exclusion Criteria**

An individual fulfilling *any* of the following criteria is to be excluded from study enrollment:

---

a “6 months to 17 years” means from the 6th month after birth to the day before the 18th birthday.

- 1) Subject is pregnant, or lactating, or of childbearing potential and not using an effective method of contraception or abstinence from at least 4 weeks prior to vaccination until at least 4 weeks after vaccination. To be considered of non-childbearing potential, a female must be pre-menarchea.
- 2) Participation at the time of study enrollment (or in the 4 weeks preceding the first study vaccination) or planned participation during the present study period in another clinical study investigating a vaccine, drug, medical device, or medical procedure.
- 3) Receipt of any vaccine in the 30 days preceding the first study vaccination, or planned receipt of any vaccine before Visit 3 for subjects receiving 1 dose of influenza vaccine or Visit 5 for subjects receiving 2 doses of influenza vaccine.
- 4) For previously influenza vaccinated subjects: Previous vaccination against influenza in the preceding 6 months with either the study vaccine or another vaccineb.
- 5) For previously influenza unvaccinated subjects: Any influenza vaccination (from birth to the day of inclusion) with either the study vaccine or another influenza vaccinec.
- 6) For previously influenza unvaccinated subjects: Any previous laboratory confirmed influenza infection (from birth to the day of inclusion).
- 7) Receipt of immune globulins, blood or blood-derived products in the past 3 months.
- 8) Known or suspected congenital or acquired immunodeficiency; or receipt of immunosuppressive therapy, such as anti-cancer chemotherapy or radiation therapy, within the preceding 6 months; or long-term systemic corticosteroid therapy (prednisone or equivalent for more than 2 consecutive weeks within the past 3 months).
- 9) Known systemic hypersensitivity to any of the vaccine components, or history of a life-threatening reaction to the vaccines used in the study or to a vaccine containing any of the same substancesa.

---

a Pre-menarche females will declare by themselves that they have not yet started menstruation. If a young female subject reaches menarche during the study, then she is to be considered as a woman of childbearing potential from that time forward.

b For the US sites, in following the ACIP Guidelines, this study will consider subjects 6 months to 8 years of age who have received at least 2 doses of seasonal influenza vaccine in prior influenza seasons as “previously influenza vaccinated subjects” when enrolling and thus these subjects will receive only 1 dose of study vaccine.

c For the US sites, in following the ACIP Guidelines, this study will consider subjects 6 months to 8 years of age who have never been vaccinated against influenza or who have not received at least 2 doses of seasonal influenza vaccine in a prior influenza season as “previously influenza unvaccinated subjects” when enrolling and thus these subjects will receive 2 doses of study vaccine at least 28 days apart. Subjects whose vaccination history is unknown will also be considered as “previously influenza unvaccinated subjects” when enrolling and also receive 2 doses of study vaccine at least 28 days apart.

For the Canadian sites, in following the NACI’s recommendations, this study will consider subjects 6 months to less than 24 months of age who have never been vaccinated against influenza in a prior influenza season as “previously influenza unvaccinated subjects” when enrolling and thus these subjects will receive 2 doses of study vaccine at least 28 days apart. Subjects who have received at least 1 dose of any influenza vaccine in the past will not be considered “previously influenza unvaccinated subjects”.

- 10) Thrombocytopenia or bleeding disorder, contraindicating IM vaccination based on Investigator's judgement.
- 11) Deprived of freedom by an administrative or court order, or in an emergency setting, or hospitalized involuntarily.
- 12) Current alcohol abuse or drug addiction.
- 13) Chronic illness that, in the opinion of the investigator, is at a stage where it might interfere with study conduct or completionb.
- 14) Moderate or severe acute illness/infection (according to investigator judgment) on the day of vaccination or febrile illness (temperature  $\geq 38.0^{\circ}\text{C}$  [ $\geq 100.4^{\circ}\text{F}$ ]). A prospective subject should not be included in the study until the condition has resolved or the febrile event has subsided.
- 15) Identified as an immediate family member (ie, spouse, natural or adopted child, grandchild, nephew, or niece) of the Investigator or employee with direct involvement in the proposed study.
- 16) Personal history of GBS.
- 17) Any condition that in the opinion of the Investigator would pose a health risk to the subject if enrolled or could interfere with the evaluation of the vaccine.
- 18) Personal history of clinically significant development delay (at the discretion of the Investigator), neurologic disorder, or seizure disorder.
- 19) Known seropositivity for hepatitis B or hepatitis C.

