### 5.1.5 Planned Study Calendar

The following dates are approximate. The actual dates may differ as, for example, the study will not start until all the appropriate regulatory and ethical approvals have been obtained.

Planned study period - FVFS (first visit, first subject) to LCLS (last contact, last subject; phone call at the end of the 6-months follow up period): 10 October 2018 – 15 October 2019

Planned inclusion period - FVFS to FVLS (first visit, last subject):

- Stage 1a: 10 October 2018 – 19 October 2018
- Stage 2: 05 November 2018 – 09 November 2018
- Stage 3: 29 November 2018 – 10 December 2018
- Stage 4: 03 January 2019 – 28 February 2019

Planned study period (active phase) – FVFS to LVLS (last visit, last subject):

- Stage 1: 10 October 2018 – 21 November 2018
- Stage 2: 05 November 2018 – 11 January 2019
- Stage 3: 29 November 2018 – 11 February 2019
- Stage 4: 03 January 2019 – 02 May 2019

Planned end of study (LCLS; phone call at the end of the 6-months follow up period): 15 October 2019

Planned date of final clinical study report: 05 March 2020

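### Criterion 5 and its own footnote c disagree on whether partly vaccinated US children may join the two-dose class; if the footnote governs, only a 30-day interval since influenza vaccine applies to them

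*Protocol*

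**What the plan says.** Protocol Section 5.2.5 has three rules that bear on earlier vaccination:

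- Criterion 3, for all subjects: "Receipt of any vaccine in the 30 days preceding the first study vaccination".
- Criterion 4, for one label only: "For previously influenza vaccinated subjects: Previous vaccination against influenza in the preceding 6 months with either the study vaccine or another vaccine".
- Criterion 5, for the other label: "For previously influenza unvaccinated subjects: Any influenza vaccination (from birth to the day of inclusion) with either the study vaccine or another influenza vaccine".

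Two footnotes then define the labels for US children aged 6 months to 8 years. Footnote b, on criterion 4, covers those "who have received at least 2 doses of seasonal influenza vaccine in prior influenza seasons as “previously influenza vaccinated subjects” when enrolling"; they get one study dose. Footnote c, on criterion 5, covers children never vaccinated and also those "who have not received at least 2 doses of seasonal influenza vaccine in a prior influenza season as “previously influenza unvaccinated subjects” when enrolling"; they get two study doses. It adds: "Subjects whose vaccination history is unknown will also be considered as “previously influenza unvaccinated subjects” when enrolling".

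Visit 1 step 8 (Section 5.1.4) contains both positions. Its opening line has the site confirm that a child labelled unvaccinated has had no seasonal influenza vaccine since birth. The note beneath it repeats footnote c. Section 5.2.7.2 describes the two-dose children as never having had any influenza vaccine before the study. For Canadian sites, any earlier dose removes the unvaccinated label.

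Step 8 asks for the month and year of the last influenza vaccination only for subjects labelled previously vaccinated.

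**The concern.** The 6-month influenza interval depends on a label, and under footnote c the label does not match what the child has received. Doses given in the current season are not doses in a prior season. A US child under 9 with one or two 2018-2019 doses and no adequate earlier history is therefore previously unvaccinated under footnote c, and criterion 4 does not apply.

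If such a child is enrolled, the D0 sample may already reflect this season's vaccine. Fold-rise and HAI seroconversion are both measured against D0, so a raised baseline works against both. The child would also be counted in the stratum meant to hold unprimed children, in a study whose stated goal is to choose a dosage for Phase III. Previous vaccination status is a randomization stratum (Protocol Section 6.5) and a possible immunogenicity subgroup (SAP Section 5.1.1.2), so its meaning matters.

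The planned data might not reveal the problem. The date of the last dose is not requested for these children, status comes from the parent or guardian, and the vaccination-history variable named in SAP Section 4.4.4.5 concerns the previous season.

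**Working it through.** The plan gives no figure to reproduce here, and the sample size is not powered. The check is a comparison of passages followed by date arithmetic.

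**1. What happens to a US child under 9 with a current-season dose more than 30 days old and fewer than 2 doses in any prior season**

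| Text taken as governing | Label | Rule that applies | Result |
|---|---|---|---|
| Criterion 5 body, Visit 1 since-birth check, Section 5.2.7.2 | Unvaccinated requires no dose ever | Lifetime bar | Excluded |
| Footnote c, Visit 1 note | Unvaccinated | Criterion 3 only (30 days) | Admitted, two study doses |

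The two rows cannot both hold. If criterion 5's body prevails, the part of footnote c about children lacking 2 doses admits nobody who has had a dose. For a child of unknown history, the since-birth confirmation cannot be made at all, yet footnote c enrols that child.

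**2. Size of the window on the footnote c reading**

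Inputs: inclusion periods in Protocol Section 5.1.5, for example "Stage 4: 03 January 2019 – 28 February 2019". Cut-offs are the inclusion date minus 30 days (criterion 3) and minus 6 calendar months (criterion 4).

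| Stage | Inclusion | 30-day cut-off | 6-month cut-off | Days between |
|---|---|---|---|---|
| 1 | 10-19 Oct 2018 | 10-19 Sep 2018 | 10-19 Apr 2018 | 153 |
| 2 | 5-9 Nov 2018 | 6-10 Oct 2018 | 5-9 May 2018 | 154 |
| 3 | 29 Nov-10 Dec 2018 | 30 Oct-10 Nov 2018 | 29 May-10 Jun 2018 | 153-154 |
| 4 | 3 Jan-28 Feb 2019 | 4 Dec 2018-29 Jan 2019 | 3 Jul-28 Aug 2018 | 154 |

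The distance between the two rules hardly changes by stage. What changes is how much of the 2018-2019 season lies before the 30-day cut-off: little in Stage 1, most in Stage 4. On criterion 5's body text the window is zero in every stage.

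**3. Groups the wording could touch** (sizes from Protocol Section 12.5)

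- Stage 1, Groups 1 and 9: 40 + 40 = 80
- Stage 2, Groups 2, 3 and 10: 40 + 40 + 40 = 120
- Stage 3, Groups 4, 5 and 11: 90 + 40 + 60 = 190
- Stage 4, Group 6: 60

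The total is 80 + 120 + 190 + 60 = 450. This is a ceiling on planned enrolment in groups that may contain the unvaccinated label, not an estimate of children affected. Group 7 takes only the vaccinated label, and Group 8 is covered by the Canadian definition.

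**4. Effect on seroconversion for one child**

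With D0 below 10, seroconversion needs a post-vaccination titer of 40. With D0 at 10 or above it needs 4 × D0. For assumed D0 titers of 20, 40 and 80 the requirement becomes 80, 160 and 320. The documents do not say what D0 titer a recent dose would leave; these values only show the direction.

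**The case against.** The strongest reply is that the eligibility text already shuts these children out. One exclusion criterion is enough, and criterion 5 bars any earlier influenza vaccine for the unvaccinated label; Visit 1's opening check and Section 5.2.7.2 agree. A reader might infer that the plan simply sets 6 months for one label and 30 days for the other. The documents do not support that: as the criteria are worded, the contrast is 6 months against a lifetime bar, and 30 days results only if footnote c overrides criterion 5. This part of the objection stands, and it makes the point conditional. It does not remove it, because footnote c is attached to criterion 5, defines its key term for enrolment, and is repeated as a site instruction at Visit 1.

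A reader might also infer that there is no washout at all. That is wrong, since criterion 3 covers every vaccine, influenza included. What would be missing is an influenza-specific interval.

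Third, the Stage 4 dates should not be applied to the 390 children planned in Groups 1-5 and 9-11 (80 + 120 + 190), who enrol in Stages 1 to 3 with earlier cut-offs.

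There is some protection in the analysis. Randomization is stratified by previous vaccination status, so affected children should fall in both arms of a group. The SAP allows subgroups by baseline serostatus and plans a baseline-adjusted sensitivity analysis of GMT ratios. Criterion 17 lets the investigator exclude a child with a condition that might interfere with evaluating the vaccine. History of seasonal influenza vaccination is listed at V01 for everyone. These limits are real but partial. Seroconversion is not baseline-adjusted, and absolute response rates in the stratum would still be affected. Comparisons with the pooled QIV-SD group also mix stages that enrol at different points in the season.

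**Conclusion.** The defect is a contradiction about eligibility, with a conditional consequence. Criterion 5, the since-birth check and Section 5.2.7.2 exclude a previously dosed child from the two-dose class; footnote c and the Visit 1 note include some of those children. If sites enrol by footnote c, criterion 4 does not reach partly vaccinated or unknown-history US children under 9, and 30 days is the only interval left. If they enrol by criterion 5's body text, the interval problem disappears.

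On the footnote reading the period allowed for one label and barred for the other is 153 to 154 days. It matters most for Group 6 (60 children) and less for the earlier stages. The conclusion assumes that some children approached had received a 2018-2019 dose more than 30 days earlier, and that such a dose raises D0 titers. The documents give neither the share of such children nor the date when the season's vaccine became available, so no number affected can be stated.

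**What to change.** Reconcile criteria 3, 4 and 5, footnotes b and c, Visit 1 step 8 and Section 5.2.7.2 so that they give one answer to three questions: whether partly vaccinated or unknown-history US children are eligible; how a dose given in the current season is classified; and which interval since the last influenza vaccine applies to any such child who is admitted. Which rule is right is for the sponsor and investigators to decide; this review does not propose one.

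Separately, record the date of the last influenza vaccine for every subject with any previous dose, so that affected children can be identified in listings and in a sensitivity analysis.

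The cost is amendment wording and the extension of one existing data item to more subjects. Depending on how the passages are reconciled, a few children who would be enrolled under the footnote may become ineligible.

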#### **5.1.4 Visit Procedures**

##### ***Visit 1 (Day 0): Inclusion, Randomization, Blood sample, and Vaccination – for all subjects***

###### **The Investigator or delegate will:**

- 1) Give the subject and / or subject's parent / guardian information about the study.
- 2) Obtain informed consent and assent (for subjects 7 to 17 years of age) and answer any questions to ensure that the subjects and/or subject's parent / guardian have been informed of all aspects of the study that are relevant to their decision to participate.
- 3) Date and sign the ICF (and assent form for subjects 7 to 17 years of age) after it has been signed and dated by the subject or subject's parent / guardian. Retain the original and give a signed copy to the subject or subject's parent / guardian.
- 4) Check all inclusion and exclusion criteria (see [Section 5.2.4](#) and [Section 5.2.5](#), respectively) through physical examination and medical interview of the subject and / or subject's parent / guardian. If the subject is not eligible, only the specific form entitled "Recruitment log" will state the subject identification, no CRB will be completed.
- 5) Collect relevant demographic information (eg, date of birth, sex, ethnicity, and race).
- 6) For females of childbearing potential, conduct a urine pregnancy test.
- 7) Obtain verbal information on medical history.
- 8) Obtain information on seasonal influenza vaccination and any influenza diagnosis as follows:
  - For previously influenza unvaccinated subjects, confirm that the subject has not been vaccinated with any seasonal influenza vaccine since birth and has never had a known influenza diagnosis.

Note: For the US sites, in following the Advisory Committee on Immunization Practices (ACIP) Guidelines, this study will consider subjects 6 months to 8 years of age who have never been vaccinated against influenza or who have not received at least 2 doses of seasonal influenza vaccine in a prior influenza season as "previously influenza unvaccinated subjects" when enrolling and thus these subjects will receive 2 doses of study vaccine at least 28 days apart. Subjects whose vaccination history is unknown will

also be considered as “previously influenza unvaccinated subjects” when enrolling and also receive 2 doses of study vaccine at least 28 days apart.

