Site staff will connect to the IRT, enter the identification and security information, and confirm a minimal amount of data in response to IRT prompts. The IRT will then provide the group assignment and have the site staff confirm it. Stratified randomization will be applied for all

subjects enrolled in each group stratified by previous influenza vaccination status and country. Site will not be a strata for randomization due to the small sample size in each group. The allocation ratios between investigational HD vaccines to the comparators are: 3:1 ratio in groups 1, 2, 3, 5, 9, and 10; 3:3:1 ratio in group 12; and 1:1 ratio in groups 4, 6, 7, 8, 11, and 13. The full detailed procedures for group allocation are described in the Operating Guidelines. If the subject is not eligible to participate in the study, then the information will only be recorded on the subject recruitment log.

Subject numbers that are assigned by the IRT will consist of a 12-digit string (a 3-digit country identifier [840 for the US and 124 for Canada], a 4-digit study site identifier, and a 5-digit subject identifier). For example, Subject 840000100005 is the fifth subject enrolled in Center Number 1 in the US.

Subject numbers should not be reassigned for any reason.

Dose numbers will be 7 digits long. Dose numbers are not used for packaging but only in the IRT system.

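### For US children aged 6 months to 8 years, the two vaccination-status definitions overlap: one dose in each of two or more earlier seasons satisfies both, and the number of study doses depends on which is applied

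*Protocol*

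**What the plan says.** The definitions appear twice: in Protocol 5.1.4 (Visit 1, step 8) and in footnotes b and c to Protocol 5.2.5. The wording is the same in both places.

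- **Previously vaccinated (US, 6 months to 8 years):** children "who have received at least 2 doses of seasonal influenza vaccine in prior influenza seasons". The consequence is that "thus these subjects will receive only 1 dose of study vaccine".
- **Previously unvaccinated (US, 6 months to 8 years):** children never vaccinated, those "who have not received at least 2 doses of seasonal influenza vaccine in a prior influenza season", and those with unknown history. The consequence is that "thus these subjects will receive 2 doses of study vaccine at least 28 days apart".

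Three other places describe the unvaccinated class more narrowly:

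- The body of exclusion 5 excludes an unvaccinated subject with "Any influenza vaccination (from birth to the day of inclusion) with either the study vaccine or another influenza vaccine".
- Visit 1, step 8, tells staff to "confirm that the subject has not been vaccinated with any seasonal influenza vaccine since birth".
- Protocol 5.2.7.2 introduces the definitive contraindications as applying to two-dose subjects with no influenza vaccine before the study.

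Protocol 6.5 has randomisation "stratified by previous influenza vaccination status and country". Under Table 5.1, status comes from the parent or guardian. Canada (Group 8) has its own definition, which does not overlap.

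**The concern.** Two definitions that sort children into one-dose and two-dose schedules should be complements. These are not, because one uses the plural for seasons and the other the singular. The pair recurs in the visit instructions, so it is not a single slip. Both notes refer to the same external guideline, so that reference cannot break the tie from the text.

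Much depends on status:

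- the number of study doses (Protocol 5.1.3);
- which of exclusions 4, 5 and 6 apply (5.2.5);
- the randomisation stratum (6.5);
- whether follow-up and endpoints end at D28 or D56 (5.1.3, 9.2.1);
- whether one or two doses are required for the immunogenicity analysis set (12.2.1; SAP 5.2.1);
- in Stage 4, whether a child enters Group 6 or Group 7 (5.1.1).

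If the wording is read in different ways, children with the same history can be assigned differently. That mixes the results by vaccination status and those after the last vaccination, both foreseen in SAP 5.1.1.2.

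**Working it through.** **1. Dose histories against the two definitions.** All histories over three earlier seasons, with 0, 1 or 2 doses in each, were tested; order does not matter. Footnote b is met if the total is at least 2. Footnote c was read in two ways: (i) no single season with 2 doses; (ii) a total below 2.

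| Doses by season | Meets b | Meets c, reading (i) | Meets c, reading (ii) | Meets both under (i) |
|---|---|---|---|---|
| none | no | yes | yes | no |
| 1 | no | yes | yes | no |
| 1+1 | yes | yes | no | **yes** |
| 1+1+1 | yes | yes | no | **yes** |
| 2 | yes | no | no | no |
| 2+1, 2+1+1, 2+2, 2+2+1, 2+2+2 | yes | no | no | no |

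Under (i), 1+1 and 1+1+1 meet both definitions, and no history meets neither. Under (ii), every history meets exactly one. The defect is therefore the mismatch between the two counting phrases.

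**2. Other text on the 1+1 child.** If classed as vaccinated, the child gets one dose and exclusion 4 applies. If classed as unvaccinated, the child gets two doses under footnote c, but fails the body of exclusion 5 and the Visit 1 check, and is not described by the opening of 5.2.7.2. The text thus supports one dose, two doses or ineligibility.

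**3. How many subjects the rule governs.** Group sizes are from Protocol 12.5.

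- Check of the stated total: 6 × 40 (Groups 1, 2, 3, 5, 9, 10) + 90 (Group 4) + 60 (Group 7) + 2 × 60 (Groups 6, 8) + 2 × 60 (Groups 11, 13) + 70 (Group 12) = 700, as stated.
- US, 6 months to 8 years: 700 − 60 (Group 8) − 70 (Group 12) − 60 (Group 13) = 510, or 72.9%.
- Of these, aged 3 to 8 years (Groups 1, 2, 4, 9, 10, 11): 40 + 40 + 90 + 40 + 40 + 60 = 310.
- Aged 6 to < 36 months (Groups 3, 5, 6, 7): 40 + 40 + 60 + 60 = 200.

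**4. How many might be affected.** The documents give no share for this history; 5% to 15% is an assumption.

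- Aged 3 to 8 years: 0.05 × 310 = 15.5 and 0.15 × 310 = 46.5, so about 16 to 47.
- Under 36 months, two earlier seasons are needed. Assume no dose before 6 months of age and a 2016-17 season ending by about June 2017. An affected child was then born by about December 2016 and is about 2 years or older at Stage 2 to 4 enrolment (November 2018 to February 2019, Protocol 5.1.5). With ages uniform over the 30-month range, 12/30 × 200 = 80 could have such a history. The base becomes 310 + 80 = 390, and 5% to 15% of it is 19.5 to 58.5, about 20 to 59.

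**5. Whether it can be repaired at analysis.** For vaccinated subjects, step 8 asks for the month and year of the last influenza vaccination. For unvaccinated subjects it asks for confirmation of no vaccination and no influenza diagnosis. Neither asks for doses per season. SAP 4.4.4.5 uses previous-season vaccination as collected, without derivation. The planned data would not reliably identify these children.

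**The case against.** The best defence is that the singular can be read cumulatively, in which case the definitions are complements. Both notes point to one named guideline, every site has both notes in front of it, and the Operating Guidelines, which we cannot see, hold the detailed allocation procedures and may settle the matter. The never-vaccinated wording in exclusion 5, step 8 and 5.2.7.2 would also keep 1+1 children out of the two-dose class. Part of this stands: the cumulative reading is possible, and actual divergence between sites is not shown. But the text does not state that reading, and footnote c itself widens the class that exclusion 5 appears to narrow, so the never-vaccinated wording adds a conflict rather than resolving one.

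Three stronger readings are tempting and not supported:

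- **That the vaccine comparison is biased.** Status is obtained at step 8, before IRT randomisation at step 12, and is a stratum. Misclassification occurs before allocation and falls alike on QIV-HD and its comparator within a stratum. The study also tests no hypotheses and is not powered.
- **That the assumed share applies to all 510.** That would give 26 to 77 (0.05 × 510 = 25.5; 0.15 × 510 = 76.5). It is inflated, because most children under 2 years cannot have had doses in two earlier seasons.
- **That Groups 6 and 7 are undetermined as a whole.** Only their older children can have such a history.

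**Conclusion.** The concern holds as a contradiction in a stated rule, not as a matter of missing detail. As worded, a US child under 9 years with one dose in each of two or more earlier seasons, and no season with two, meets both definitions; the remaining text could also make that child ineligible. The harm is to consistent eligibility and dose assignment, and to the reading of results by vaccination status and after the last vaccination.

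The number affected is unknown. The range of about 16 to 47 at 3 to 8 years rests wholly on the assumed share. The addition for older children under 36 months (to about 20 to 59 in all) rests further on the age and season assumptions shown. Because the rule decides how many doses of an investigational vaccine a child receives, it should give one answer whatever that number is.

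**What to change.** Reconcile Protocol 5.1.4 (Visit 1, step 8, both US notes and the since-birth check), 5.2.5 (the body of exclusion 5 and footnotes b and c) and 5.2.7.2. Use the same counting phrase throughout, so that every child meets exactly one definition and a child placed in a class is not excluded by that class's own criterion. Which count applies is for the sponsor's clinical team.

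At V01, record the number of prior influenza vaccine doses and the season of each. Have IRT derive the stratum, and in Stage 4 the choice between Groups 6 and 7, from that entry. Use the derived status in the SAP subgroup analyses.

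The cost is a protocol amendment touching several notes, and one added data entry field. The field is new collection, because step 8 now asks vaccinated subjects only when they were last vaccinated. Vaccination history is already taken at V01, so no extra visit is needed.
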